10.6.1 Estimating Severity Grade for Parameters Not Identified in the Grading Table

The functional table below should be used to grade the severity of an AE that is not specifically identified in the grading table. In addition, all deaths related to an AE are to be classified as **Grade 5**

PARAMETER	GRADE 1 MILD	GRADE 2 MODERATE	GRADE 3 SEVERE	GRADE 4 POTENTIALLY LIFE-THREATENING
Clinical adverse event NOT identified elsewhere in the grading table	Mild symptoms causing no or minimal interference with usual social & functional activities with intervention not indicated	Moderate symptoms causing greater than minimal interference with usual social & functional activities with intervention indicated	Severe symptoms causing inability to perform usual social & functional activities with intervention or hospitalization indicated	Potentially life-threatening symptoms causing inability to perform basic self-care functions with intervention indicated to prevent permanent impairment, persistent disability, or death

10.6.2 QTc prolongation using the Fridericia formula

The DAIDS AE Grading Table provides grading for QTc prolongation using the Bazett formula. When the Fridericia formula is used, QTc prolongation should be graded as shown:

Severity Grade 1	460 msec or greater but less than 480msec
Severity Grade 2	480 msec or greater but less than 500 msec
Severity Grade 3	500 msec or greater OR 60 msec or greater than baseline AND 480 msec or greater
Severity Grade 4	Life-threatening consequences (e.g., Torsades de Pointes, other serious ventricular dysrhythmias)

10.7 Appendix 7 : CDC Classification for HIV-1 Infection

Note that the CD4+ T-lymphocyte count takes precedence over the CD4+ T-lymphocyte percentage in HIV infection stages 1, 2, and 3. The CD4+ T-lymphocyte percentage should only be considered if the count is missing.

HIV infection, stage 0

Indicates early HIV infection, inferred from a negative or indeterminate HIV test result within 180 days of a positive result. The criteria for stage 0 supersede and are independent of criteria used for other stages.

HIV infection, stage 1

Laboratory confirmation of HIV infection with no AIDS-defining condition, and

- CD4+ T-lymphocyte count of ≥ 500 cells/ μ L, or
- CD4+ T-lymphocyte percentage of total lymphocytes of $\geq 26\%$.

HIV infection, stage 2

Laboratory confirmation of HIV infection with no AIDS-defining condition, and

- CD4+ T-lymphocyte count of 200 to 499 cells/ μ L, or
- CD4+ T-lymphocyte percentage of total lymphocytes of 14% to 25%.

HIV infection, stage 3 (AIDS)

Laboratory confirmation of HIV infection, and

- CD4+ T-lymphocyte count of < 200 cells/ μ L, or
- CD4+ T-lymphocyte percentage of total lymphocytes of $< 14\%$, or
- Documentation of an AIDS-defining condition (see below).

Documentation of an AIDS-defining condition supersedes a CD4+ T-lymphocyte count of > 200 cells/ μ L and a CD4+ T-lymphocyte percentage of total lymphocytes of $> 14\%$.

HIV infection, stage unknown

Laboratory confirmation of HIV infection, and

- No information on CD4+ T-lymphocyte count or percentage, and
- No information on presence of AIDS-defining conditions.

Stage-3-defining opportunistic illnesses in HIV infection

- Candidiasis of bronchi, trachea, or lungs

- Candidiasis of esophagus
- Cervical cancer, invasive
- Coccidioidomycosis, disseminated or extrapulmonary
- Cryptococcosis, extrapulmonary
- Cryptosporidiosis, chronic intestinal (>1 month's duration)
- Cytomegalovirus disease (other than liver, spleen, or nodes), onset at age >1 month
- Cytomegalovirus retinitis (with loss of vision)
- Encephalopathy, HIV-related
- Herpes simplex: chronic ulcers (>1 month's duration) or bronchitis, pneumonitis, or esophagitis (onset at age >1 month)
- Histoplasmosis, disseminated or extrapulmonary
- Isosporiasis, chronic intestinal (>1 month's duration)
- Kaposi's sarcoma
- Lymphoma, Burkitt's (or equivalent term)
- Lymphoma, immunoblastic (or equivalent term)
- Lymphoma, primary, of brain
- Mycobacterium avium complex or Mycobacterium kansasii, disseminated or extrapulmonary
- Mycobacterium tuberculosis of any site, pulmonary, disseminated or extrapulmonary
- Mycobacterium, other species or unidentified species, disseminated or extrapulmonary
- Pneumocystis jirovecii pneumonia
- Pneumonia, recurrent
- Progressive multifocal leukoencephalopathy
- Salmonella septicemia, recurrent
- Toxoplasmosis of brain, onset at age >1 month
- Wasting syndrome attributed to HIV.

Source: [CDC, 2014]

1. INTRODUCTION

The purpose of this SAP is to describe the planned analyses to be included in the CSR for Study 218806. Details of the planned interim analysis, as well as the final analyses, are provided.

1.1. Objectives, Estimands and Endpoints

Objectives	Endpoints
Primary	

 To evaluate the antiviral activity of orally administered VH4524184 in TN participants with HIV-1 during 10 days of monotherapy 	
 Maximum change from baseline (Day 1) in plasma HIV-1 ribonucleic acid (RNA) through Day 10.
Secondary	

 To assess the safety and tolerability of orally administered VH4524184 	
 Incidence of adverse events (AEs), severity of AEs and proportion of participants who discontinue treatment due to AEs. Change from baseline and maximum toxicity grade increase from baseline for liver panel laboratory parameter (Alanine Transaminase (ALT), Aspartate aminotransferase (AST), total bilirubin, direct bilirubin, alkaline phosphatase, albumin and total protein)

 To characterize the pharmacokinetic profile of orally administered VH4524184 	As data permits, PK measures that include: 
 Maximum observed plasma drug concentration (Cmax), Time to maximum observed plasma drug concentration (tmax), Concentration on Day 10

 To evaluate any relationship between VH4524184 exposure and change in plasma HIV1 RNA 	
 Correlation of VH4524184 PK parameters with maximum plasma HIV-1 RNA change from baseline through Day 10

 To assess the occurrence of emergent genotypic or phenotypic resistance after 10 days of monotherapy with VH4524184 	
 Genotypic and phenotypic data from baseline (Day 1) and Day 10 will be compared for amino acid substitutions and VH4524184 fold change IC50.

 To assess the immunologic effects of VH4524184 when administered over 10 days in participants living with HIV 	
 Change from baseline in CD4+ T-cell count to Day 10
Tertiary	

Objectives	Endpoints

 To further assess the safety and tolerability of orally administered VH4524184 	
 Post baseline values and changes over time of vital signs, electrocardiogram (ECG) parameters and suicidality scores. Absolute values, change from baseline and maximum toxicity grade increase from baseline for hematology, coagulation and remaining chemistry panels

Primary estimand

The primary objective is to evaluate the antiviral activity of orally administered VH4524184 in TN participants with HIV-1 during 10 days of monotherapy.

The estimand is described by the following attributes:

- Population:**
Overtly healthy (other than HIV-1 infection) treatment naïve individuals
- Endpoint:**
Maximum change from baseline (Day 1) in plasma HIV-1 RNA through Day 10
- Treatment:**
VH4524184 or placebo CCI
- Intercurrent events:**
 - Discontinuation of study treatment due to any reason will be addressed using **while on-treatment strategy**, i.e. any HIV-1 RNA data available after study treatment discontinuation day + 1 and prior to starting standard of care (SOC) will be excluded from calculation of max VLD
 - Use of SOC or other antiviral medication prior to Day 10 will be addressed using **while on-treatment strategy**, i.e., HIV-1 RNA collected after initiation of SOC, if for any reason this takes place prior to Day 10, will be excluded from calculation of max VLD
 - Use of prohibited medication will be addressed using **treatment policy strategy**, i.e., any HIV-1 RNA data available after use of prohibited medication will be used in calculation of max VLD
 - CCI
- Population-level summary:**

Mean of maximum change from baseline in log10 HIV-1 RNA during Days 1-10

Rationale for estimand: Interest lies in evaluating efficacy of orally administered VH4524184 **CCI** or use of prohibited medications and not in combination with other antiretroviral medication.

Secondary estimands

The secondary objective is to assess the safety and tolerability of orally administered VH4524184.

The estimand is described by the following attributes:

- **Population:**

Overtly healthy (other than HIV-1 infection) treatment naïve individuals

- **Endpoint:**

- Incidence of AEs, severity of AEs and proportion of participants who discontinue treatment due to AEs
- Change from baseline and maximum toxicity grade increase from baseline for liver panel laboratory parameter

- **Treatment:**

VH4524184 or placebo **CCI** followed by SOC on Days 10-38

- **Intercurrent events:**

- Discontinuation of study treatment due to any reason will be addressed using **treatment policy strategy**, i.e. all safety data after study treatment discontinuation will be used
- Use of SOC or other antiviral medication prior to Day 10 will be addressed using **while on-treatment strategy**, i.e., safety data collected after initiation of SOC, if for any reason this takes place prior to Day 10, will be excluded from monotherapy safety summaries
- Use of prohibited medication will be addressed using **treatment policy strategy**, i.e., all safety data will be used regardless of the use of prohibited medication

• **CCI**

- **Population-level summary:**

AEs:

- Number and percentage of participants with AEs
- Number and percentage of participants with AEs by severity grade
- Number and percentage of participants with AEs leading to study treatment discontinuation

Liver panel laboratory parameters:

- Summary statistics (mean, SD, median, min, max, etc.) of change from baseline
- Number and percentage of participants with maximum toxicity grade increase relative to baseline

Rationale for estimand: Interest lies in evaluating safety and tolerability of orally administered VH4524184 irrespective of study treatment discontinuation, **cci** [REDACTED], or use of prohibited medications and not in combination with other antiretroviral medication.

Another secondary objective is to characterize the PK profile of orally administered VH4524184.

The estimand is described by the following attributes:

- **Population:**
Overtly healthy (other than HIV-1 infection) treatment naïve individuals
- **Endpoints:**
As data permits,
 - Maximum observed plasma drug concentration (Cmax)
 - Time to maximum observed plasma drug concentration (tmax)
 - Concentration on Day 10
- **Treatment:**
VH4524184 or placebo **cci** [REDACTED] followed by SOC on Days 10-38
- **Intercurrent events:**
 - Discontinuation of study treatment due to any reason will be addressed using **while on-treatment strategy**, i.e. PK data after study treatment discontinuation will be excluded from use in noncompartmental analyses.
 - Use of SOC or other antiviral medication prior to collection of HIV-1 RNA and PK specimens on Day 10 will be addressed using **while on-treatment strategy**, i.e., PK data collected after initiation of SOC, if for any reason this takes place prior to Day 10, will be excluded

- Use of prohibited medication will be addressed using **treatment policy strategy**, i.e., all PK data will be used regardless of the use of prohibited medication
- **CCI** of study treatment will be addressed using **while on-treatment strategy**, i.e. PK data collected **CCI** will be excluded from use in noncompartmental analyses.
- **Population-level summary:**

Summary statistics (e.g. arithmetic mean, SD, median, min, max, geometric mean, SD (log), %CVb, etc.)

Rationale for estimand: Interest lies in characterizing the PK profile of orally administered VH4524184 which could be biased by study treatment discontinuation, **CCI**, or use of SOC medication prior to day 10.

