5.2.2. Prior/Concomitant Therapy

12. Treatment with immunomodulating agents (such as systemic corticosteroids, interleukins, interferons) or any agent with known anti-HIV activity (such as hydroxyurea or foscarnet) within 30 days of study drug administration.
13. Past or intended use of over-the-counter or prescription medication including herbal medications within 7 days (or 14 days if the drug is a potential enzyme inducer) or 5 half-lives (whichever is longer) prior to dosing. Specific medications listed in Section 6.9.1 may be allowed.
14. History of sensitivity to any of the study medications, or their components or drugs of their class, or a history of drug hypersensitivity (including delayed hypersensitivity or severe hypersensitivity reactions) or other allergy that, in the opinion of the investigator or Medical Monitor, contraindicates their participation.
15. Participants who require concomitant medications known to be associated with a prolonged QTc.
16. Participants receiving any protocol-prohibited medication(s) and who are unwilling or unable to switch to an alternate medication (See Section 6.9.2).

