6.9.2 Prohibited Medications

See Section [5.2.2](#).

CCI

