4.2. Primary Endpoint(s) Analyses

4.2.1. Definition of endpoint(s)/estimands

See section 1.1 for definition of primary endpoint/estimand.

Change from baseline at the time point where the HIV-1 RNA is minimum (nadir) during the monotherapy period will be calculated for each participant in the original and \log_{10} scales. The change from baseline at nadir is the primary endpoint used to construct the primary estimand (see section 1.1). According to primary estimand definition (section 1.1), if SoC medication starts prior to Day 10 (for any reason), change from baseline values after SoC initiation will be excluded from calculation of change from baseline at nadir.

Note, the change from baseline at nadir during monotherapy is typically the maximum change from baseline in HIV-1 RNA, or in other words the maximum Viral Load Decline (VLD). However, for participants who have all their post-baseline HIV-1 RNA values during monotherapy higher than the baseline value (e.g. as is the potential with some participants randomized to placebo) the change from baseline at nadir is the minimum change from baseline. Also, if a (placebo) participant has a high increase from baseline in HIV-1 RNA and then a smaller decrease from baseline (or vice versa), the maximum change from baseline is at the point where HIV-1 RNA is its peak (zenith); the change from baseline at nadir will be used in this case in the primary analysis. From now on, in this document by “maximum change from baseline in HIV-1 RNA” during monotherapy we will mean the “change in HIV-1 RNA at nadir”.

The \log_{10} transformation is used to allow for direct comparisons with data from other compounds publicly available in the same scale, and hence aid in interpretation.

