4.2.2. Main analytical approach

The primary efficacy analysis will be based on the Full Analysis Set.

Maximum change from baseline in plasma HIV-1 RNA during monotherapy will be summarized in original and \log_{10} scales using descriptive statistics as described in section 4.1.1.

In addition, change from baseline in plasma HIV-1 RNA at each assessment time point during monotherapy will be summarized in original and \log_{10} scales.

Any missing HIV-1 RNA data (e.g., due to missed visits in the clinic, loss to follow-up or for any other reason) will not be imputed and will remain missing. Whatever HIV-1 RNA data are available for a participant during monotherapy and prior to starting SoC will be used to calculate maximum VLD.

If a participant withdraws from study prior to the end of monotherapy period, preventing assessment of primary endpoint, no imputation will be performed for missed assessments after their study withdrawal.

All HIV-1 RNA data from all participants will be included in RAPIDO DV

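### The primary estimand covers any antiviral taken before Day 10, but the SAP's working rules exclude HIV-1 RNA only after SoC starts, and the visible prohibited-medication rule can point the other way

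*SAP*

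**What the plan says.** Protocol 3.1.1 and SAP 1.1 define the primary estimand in matching terms. Two of the intercurrent-event bullets matter here.

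- **SoC or other antiviral.** The bullet opens "Use of SOC or other antiviral medication prior to Day 10 will be addressed using" and names a while-on-treatment strategy. Its explanation then reads "HIV-1 RNA collected after initiation of SOC, if for any reason this takes place prior to Day 10, will be excluded from calculation of max" (that is, from the maximum viral load decline). Only SoC appears in that explanation.
- **Prohibited medication.** The strategy is treatment policy: "any HIV-1 RNA data available after use of prohibited medication will be used in calculation of max VLD". No exception for anti-HIV agents is visible.

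The stated rationale is to learn what VH4524184 does without other antiretrovirals.

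Protocol 6.9.2 sends the reader to 5.2.2, and the remainder of 6.9.2 is redacted. Criterion 12 in 5.2.2 names "any agent with known anti-HIV activity (such as hydroxyurea or foscarnet) within 30 days of study drug administration".

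The SAP turns the estimand into a derivation in two places. SAP 4.2.1 says that "if SoC medication starts prior to Day 10 (for any reason), change from baseline values after SoC initiation will be excluded". SAP 4.2.2 says: "Whatever HIV-1 RNA data are available for a participant during monotherapy and prior to starting SoC will be used to calculate maximum VLD". SAP 6.2.2 ends the monotherapy period when SoC ART starts.

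**The concern.** The heading of the first bullet promises that HIV-1 RNA measured under another antiviral will not count. None of the visible rules that a programmer would follow delivers this unless the antiviral is SoC. A non-SoC agent with anti-HIV activity can also meet the description of a prohibited medication, for which later values are kept, and no sentence says which bullet takes precedence.

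The endpoint makes this more than a wording matter. It is the change at nadir, so a single later sample can set a participant's value. The groups are very small: 6 active participants per cohort and a pooled placebo group of 3, or 4 if Part 2 runs. If the gap were met in practice, a fall partly caused by another agent would be credited to VH4524184 or to placebo. The choice of rule would then be made after the data had been seen, in a study where the sponsor is unblinded.

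**Working it through.** The documents give no figure on this point, so the check is mainly textual.

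**Step 1. Which event ends the use of HIV-1 RNA?**

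| Place | Cut-off in the visible text |
|---|---|
| Protocol 3.1.1 and SAP 1.1, bullet heading | SoC or other antiviral |
| Same bullet, explanation | SoC only |
| SAP 4.2.1, derivation | SoC only |
| SAP 4.2.2, data used | SoC only |
| SAP 6.2.2, end of monotherapy | SoC ART only |
| SAP 3.1, per-protocol criterion 05 | SoC only |

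Only the heading covers other antivirals. Protocol Section 9 gives the SAP priority where methods differ, so the protocol does not correct the SAP.

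**Step 2. Can the same agent meet the opposite rule?** The chain runs from the prohibited-medication bullet to Protocol 6.9.2, then to 5.2.2, then to criterion 12 (agents with anti-HIV activity). On the visible text it can.

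**Step 3. A worked case.** The schedule shows post-baseline HIV-1 RNA on Days 2, 4, 7 and 10. Suppose a non-SoC anti-HIV agent is first taken on Day 5. Under the bullet heading, the nadir comes from Days 2 and 4. Under SAP 4.2.2, it comes from all four days.

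**Step 4. Does the per-protocol repeat catch it?** SAP 4.2.3 says that no primary intercurrent event can occur in the per-protocol set. Criterion 05 does not secure this for a non-SoC agent. Removal would depend on applying an entry criterion during treatment (criterion 07) or on case-by-case adjudication (criterion 08). Criterion 06 is redacted.

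**Step 5. Illustrative size.** Assume that one participant's nadir is deepened by x log10 and the others are unaffected. The shift in the group mean is x / n.

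| Group | x = 1 | x = 2 |
|---|---|---|
| Pooled placebo, Part 1 (n = 3) | 1/3 = 0.33 | 2/3 = 0.67 |
| Pooled placebo with Part 2 (n = 4) | 1/4 = 0.25 | 2/4 = 0.50 |
| One active dose group (n = 6) | 1/6 = 0.17 | 2/6 = 0.33 |

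The values of x are assumptions. Protocol 4.3 puts the maximum reduction seen in earlier studies at about 2 to 2.5 log10. An active participant close to that level has little further to fall, so the last row is an upper limit.

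**The case against.** The strongest reply is that this is a drafting ambiguity about a remote event, and that the intent is already clear.

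- **Redaction.** Most of 6.9.2, one intercurrent-event bullet and per-protocol criterion 06 are hidden, and a carve-out may sit there. Criterion 12 is an entry rule with a 30-day look-back. Criterion 16 in the same section names protocol-prohibited medication separately and points back to 6.9.2, so the cross-reference is circular. This stands as a limit: the overlap is shown for the visible text only.
- **Intent.** The rationale separates prohibited medication from other antiretrovirals, and the antiviral bullet is the more specific rule. This also stands. Exclusion is very probably what was meant, which is a reason to write it into the derivation.
- **SAP 4.2.1 is not exhaustive.** It refers back to SAP 1.1 and also omits the cut-off after treatment discontinuation. That is fair for 4.2.1. It does not dispose of 4.2.2, which states which data will be used. That sentence sits in a paragraph on missing data, but it is still the only explicit data rule in the main analysis section.
- **Most real cases are covered.** SoC is the regimen the investigator chooses, so ART that the investigator starts early would ordinarily be SoC. SAP 6.1.1 also counts any recorded concomitant antiretroviral start as entry to Follow-Up. The first part stands and makes the gap narrow. The second is a disposition rule, and it would not reach agents such as the two examples in criterion 12.

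A reader might infer that declines caused by other drugs do enter the primary endpoint, or that treatment policy was chosen for antivirals. The documents support neither. The first needs such an agent to be taken and a later sample to be the nadir. The second runs against the bullet heading and the rationale.

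**Conclusion.** The point holds as an inconsistency between the estimand and its derivation. The visible SAP rules do not implement the exclusion of other antivirals that the estimand announces, and the visible text gives no precedence over the prohibited-medication rule. If a participant took a non-SoC agent with anti-HIV activity before Day 10, the derivation as written would keep the later values.

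The practical weight is low. The event should be rare over 10 days in overtly healthy adults, although the documents give no frequency. The analysis is descriptive, with no hypothesis test. The pooled placebo group is the most exposed: the shift in its mean would be 0.33 to 0.67 log10 with 3 participants, or 0.25 to 0.50 with 4. In an active group of 6 it would be at most 0.17 to 0.33, and probably much smaller near maximal response. These figures rest on one affected participant, an assumed extra fall of 1 to 2 log10, and the affected sample being the nadir. The conclusion also assumes that no redacted text already contains the exception.

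**What to change.** Change the analysis rule only; no clinical rule is involved.

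1. In Protocol 3.1.1 and SAP 1.1, state that HIV-1 RNA collected after first use of SoC or of any other non-study agent with anti-HIV activity is excluded from the maximum decline. Limit the treatment-policy bullet to prohibited medications without anti-HIV activity.
2. Use the same cut-off in SAP 4.2.1 and 4.2.2.
3. Align SAP 6.2.2 and per-protocol criterion 05, so that the statement in SAP 4.2.3 about the per-protocol set holds for this event.

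If redacted text already contains this exception, steps 2 and 3 are still needed to bring the derivation into line.

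The cost is a few sentences. Concomitant medications and their start and stop dates are already collected under Protocol 6.9, so no new data are needed, and sample size and trial conduct do not change.
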